Impact of E-Cigarette Prevention Messages on Adolescents

Study Protocol

NCT#05985538

Version Date: 6/25/2020

Participants

We recruited adolescents living in the United States (US) from a national probability-based panel administered by NORC. This panel consists of households randomly selected from a sample frame, with a known, non-zero probability of selection from NORC's National Frame. The frame provides at least 97% sample coverage of the US population by supplementing the US Postal Service Delivery Sequence File. To recruit adolescents aged 13-17, NORC first contacted a parent or guardian to obtain parental consent, followed by eligible adolescents being invited to participate in the study. Young adults aged 18-20 were invited directly to participate. The eligibility criteria included: being aged 13 to 20 years, possessing a phone capable of sending and receiving text messages, and either having used e-cigarettes or vapes in the past 30 days or being susceptible to vaping. Susceptibility was defined as answering anything other than "definitely not" or "not at all curious" to any of five susceptibility questions that were answered on four-point scales (1 = *Definitely not*, 4 = *Definitely yes*; 1 = *Not at all curious*, 4 = *Very curious*). An example item is, "Do you think you might use an e-cigarette or vape soon?" Our target sample size was 506, accounting for up to 20% loss to follow-up. The trial had 80% power to detect an effect size of $d=.28$ or larger between the intervention arm and the control arm.

Recruitment took place from February 5 to June 2 of 2024. For adolescents aged 13-17, legal parents or guardians provided informed parental consent online, and adolescents provided assent online before beginning the surveys. For young adults aged 18-20, participants provided informed consent online before beginning the surveys. Of the 733 adolescents and young adults screened, 183 were ineligible because they were not susceptible to vaping; 53 were ineligible because they did not have a phone that sends and receives text messages; 11 were ineligible because they lived in the same household as a current or prior study participant; and 6 met

criteria but declined to participate (Figure 1). This resulted in a total of $N=480$ adolescents and young adults enrolled in the trial. The trial was approved by the University of North Carolina Institutional Review Board and is registered at [clinicaltrials.gov](https://clinicaltrials.gov/ct2/show/NCT05985538), identifier NCT05985538 (<https://www.clinicaltrials.gov/ct2/show/NCT05985538>). This paper follows CONSORT reporting guidelines for RCTs.

Procedures

Trial design and protocol. We conducted a two-arm randomized controlled trial (RCT) with parallel assignment. At the start of the trial, participants were randomly assigned to either *Breaking Vape*, a vaping prevention text message program (intervention arm) or to *Texting for Wellness*, a wellness text message program (attention control arm). Randomization was performed without replacement using simple randomization methods based on random numbers generated *R* Studio version 4.0.4. Due to the nature of the interventions being administered online, the research team was not blinded post-assignment.

Participants in both trial arms received at least one (but typically two) text messages per day over a 28-day period, with introductory messages sent on day 1 and concluding messages sent on day 28. The messages sent on days 2 – 27 focused on a series of topics in the intervention (negative consequences of using e-cigarettes and vaping) or attention control (wellness information) arms. To enhance engagement in both trial arms, some messages prompted replies from participants through multiple-choice quizzes and true/false questions (i.e., two-way messages). Additionally, some messages included website links to supplement the text message program information. For the intervention arm, we developed a website specifically for this study (<https://www.breakingvape.org>), while for the control arm, we provided links to existing teen wellness websites (e.g., <https://kidshealth.org/>). The structure of the intervention and control

arms were matched on the 28-day duration of the program and the number and types of two-way messages sent. In both intervention and control arms, messages were sent at approximately 4 p.m. local time. For multiple-choice quizzes and true/false questions, if participants did not respond, the correct answer was sent to them at approximately 7 p.m. local time. Consistent with the rules required by cell phone carriers, participants could opt out of receiving messages at any time by texting “Stop” and could rejoin the program by texting “Start.” A technical document describing the text messaging programs is included in the supplemental file.

To assess primary and secondary outcomes, participants completed four online surveys at four intervals: baseline, mid-intervention (2 weeks; survey was open from days 12 - 16), end of intervention (4 weeks; survey was open from days 29 - 36), and follow-up (8 weeks; survey was open from days 57 - 70). These surveys were sent by NORC via email, with text message reminders as needed (reminders were sent from a different number than the intervention messages). Incentives were offered in the form of points, redeemable for a total cash equivalent of up to \$120 upon completing the trial (\$20 for the first survey, \$25 for each of the second and third surveys, \$30 for the final survey, and \$1 for each text message response, up to \$20).

Intervention messages. Each vaping prevention text message in the *Breaking Vape* program focused on one of six topics. The program was designed so that messages about three topics were delivered before the wave 2 survey: nicotine addiction (days 2 – 5), monetary costs of vaping (days 6 – 8), chemical exposures from e-cigarette vapor (days 9 – 13); messages about the other three topics were delivered after the wave 2 but before wave 3 survey: cosmetic effects of vaping (days 14 – 16), mental and physical use symptoms of vaping (days 17 – 22), and health impact on organs from vaping (days 23 – 27). These topics were selected based on a series of studies that examined which vaping prevention content most resonated with youth.^{1,2} This

process culminated in the testing of a series of text statements that were subsequently adapted for the vaping prevention intervention.³ An example message from *Breaking Vape* is “True or false? Vaping is much less addictive than smoking cigarettes.” If a participant texted “True” (the incorrect answer), the program would respond with: “Actually, false is the right answer. Vaping can be as addictive as smoking cigarettes, and some vaping devices have even more nicotine than cigarettes. That’s why vaping is so easy to get hooked on.”

Attention control messages. Each wellness text message in the *Texting for Wellness* program focused on one of six topics, in the following order: sleep hygiene, safe driving, sun safety, study habits, nutrition, and exercise. These were chosen as they were relevant to youth but were unrelated to substance use behaviors, with content adapted from several youth-oriented wellness websites. An example message from *Texting for Wellness* is “True or false? People who eat breakfast do better in school.” If a participant texted “True” (the correct answer), the program would respond with: “You got it! Breakfast is an important part of your morning, and fueling your body before school can help you perform better.”

Text message delivery. A total of 27,840 text messages were intended to be sent out during the study. Because of intermittent technical issues in text message delivery, as well as a modest number of participants texting “stop” during the study (which halted all text message delivery unless participants texted restart), not all messages were delivered. In total, 26,100 messages were successfully delivered, representing a 93.8% fidelity rate (26,100/27,840). Text message delivery did not differ by trial arm, with a fidelity rate of 93.6% for *Breaking Vape* messages and 93.9% for attention control messages.

Intervention engagement. Of the text messages sent out, 20 of them asked for a response from the participant. Across all participants, the number of responses varied from 0 – 20 ($M=$

12.33, $SD=7.56$; $Median=16$). The number of responses was similar between *Breaking Vape* ($M=12.19$, $SD=7.71$, $Median=16$) and attention control ($M=12.46$, $SD=7.41$; $Median=16$) trial arms. Across conditions, a small proportion of participants did not respond to any messages, including 16.7% ($n=40$) in *Breaking Vape* and 12% ($n=29$) in the attention control group. In addition, we asked participants (in the 2 and 4-week surveys) how many of the text messages they read, on a 5-point response scale: 1 (none), 2 (a few), 3 (some), 4 (most), or 5 (all). In the first 2 weeks of the text-messaging, 88.1% in the *Breaking Vape* trial arm and 83.7% in the attention control arm reported reading “most” or “all” of the messages, while in the latter 2 weeks of the text-messaging, 85.5% in the *Breaking Vape* trial arm and 83.9% in the attention control arm reported reading “most” or “all” messages. We also asked participants how many of the weblinks in the text messages they visited. In the first 2 weeks of the text-messaging, 60.6% in the *Breaking Vape* trial arm and 47.2% in the attention control arm reported visiting at least one (of three possible) weblinks embedded in the text messages, while in the latter 2 weeks, 65.6% in the *Breaking Vape* trial arm and 57.6% in the attention control arm reported visiting at least one (of three) possible weblinks.

Measures

At baseline, participants reported vaping and smoking behaviors, susceptibility to vaping and smoking, vaping and smoking attitudes and beliefs, and demographic characteristics. At mid-intervention (wave 2 survey, at 2 weeks) and end of intervention (wave 3 survey, at 4 weeks), participants reported vaping and smoking behaviors, susceptibility to vaping and smoking, vaping and smoking attitudes and beliefs, and questions about reading and engaging with the text messages. At follow-up (wave 4 survey, 8 weeks after baseline), participants

reported vaping and smoking behaviors, susceptibility to vaping and smoking, and vaping and smoking attitudes and beliefs.

Primary outcome. Susceptibility to vaping at the end of text messaging (wave 3 survey, at 4 weeks) was the primary trial outcome. Susceptibility prospectively predicts vaping behavior,^{4,5} including when operationalized as a scaled score where higher values predict both greater initiation and current use of vapes.⁴ We assessed susceptibility with a 3-item susceptibility to vaping scale, similar to other studies.⁶⁻⁹ This scale assesses the extent to which adolescents are open to vaping, with a 4-point response scale ranging from “definitely not” (coded as 1) to “definitely yes” (coded as 4). We calculated a susceptibility score by averaging the 3 items, with higher scores representing higher susceptibility to vaping (Cronbach’s α at baseline =.94).

Secondary outcomes. The survey assessed several secondary outcomes hypothesized to elicit behavior change, according to the reasoned action approach¹⁰. Response scales for secondary outcomes had five points, coded such that higher scores represented a greater amount of the construct. For multi-item scales, overall scale scores were of the average of the items.

Vaping outcomes. Three-item scales assessed instrumental attitudes toward vaping ($\alpha=.89$), affective attitudes toward vaping ($\alpha=.89$), vaping addiction risk beliefs ($\alpha=.86$, vaping monetary cost beliefs ($\alpha=.94$), vaping chemical risk beliefs ($\alpha=.93$, vaping cosmetic risk beliefs ($\alpha=.90$), vaping physical symptoms of use beliefs ($\alpha=.85$), vaping mental health symptoms of use beliefs ($\alpha=.93$), vaping health organ risk beliefs ($\alpha=.91$), vaping injunctive norms ($\alpha=.92$), and vaping refusal self-efficacy beliefs ($\alpha=.91$),¹¹⁻¹⁶. Participants were also asked to report the number of days they vaped over the past 30 days. Higher scores indicated more positive attitudes towards vaping, greater belief in the harms of vaping, a stronger perception of others’ disapproval of vaping, and a greater belief in one’s ability to refuse vaping in social situations.

Smoking outcomes. Susceptibility to smoking cigarettes was assessed with a 3-item scale ($\alpha=.93$)¹⁷. Single items assessed smoking addiction risk belief, health harm risk belief, smoking instrumental attitudes and affective attitudes^{11,16}. Participants also reported the number of days they smoked cigarettes and used other tobacco products over the past 30 days.

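### Must the SAP mark the wave 2 effect on past-30-day vaping and smoking counts as resting on a partly pre-message recall window?

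*Protocol*

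**What the plan says.** **Outcome.** Under Secondary outcomes, the Protocol's Vaping outcomes paragraph states: "Participants were also asked to report the number of days they vaped over the past 30 days". The Smoking outcomes paragraph gives cigarettes and other tobacco products the same 30-day look-back.

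**When it is collected.** Protocol, Measures: "At mid-intervention (wave 2 survey, at 2 weeks) and end of intervention (wave 3 survey, at 4 weeks), participants reported vaping and smoking behaviors". That sentence does not name other tobacco products, and neither paragraph on the counts says at which waves the 30-day item was asked.

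**Timing of messages and surveys.** Protocol, Procedures, describes messaging over 28 days, "with introductory messages sent on day 1 and concluding messages sent on day 28", with topic content on days 2 to 27. The wave 2 survey is described as "mid-intervention (2 weeks; survey was open from days 12 - 16". Wave 3 could be answered on days 29 to 36 and wave 4 on days 57 to 70. Under Intervention messages, three topics are placed before the wave 2 survey, and "messages about the other three topics were delivered after the wave 2 but before wave 3 survey".

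**Analysis.** SAP, Outcome models, applies one latent curve model to susceptibility and the secondary outcomes. The effect of study condition at each of waves 2, 3 and 4 is the sum of its effect on the intercept and its effect on the slope for that wave. SAP, Statistical Analysis, sets a two-sided .05 level for everything.

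**The concern.** Taken together, these statements give a wave 2 treatment effect on a count that looks back 30 days from a survey held 12 to 16 days into the program. About half or more of the recalled days come before any message, and no message can have changed behavior on those days. The estimate would stand in the same table as those for waves 3 and 4, under the same significance rule, with nothing to show that its window differs.

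Two misreadings are possible. A null result at wave 2 could be taken to mean that the program had no early effect. A larger effect at wave 3 could be taken as an effect that grows, although the recall window alone can produce that pattern. Three of the six topics come mainly after wave 2, so real growth is also plausible, and these counts could not separate the two. The day counts are the trial's direct measures of behavior, so the point deserved a check.

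**Working it through.** **Inputs.** First message on day 1, first topic message on day 2, last message on day 28; surveys open on days 12–16, 29–36 and 57–70 (Protocol, Procedures). Recall of 30 days (Protocol, Secondary outcomes).

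**Step 1: days in each window.** For a survey answered on day *d*, the window is days *d* − 30 to *d* − 1 if the survey day is left out, or *d* − 29 to *d* if it is counted. The days before day 1 number 31 − *d* or 30 − *d*, and never fewer than 0.

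- Wave 2: 31 − 12 = 19 down to 31 − 16 = 15, or 18 down to 14. Overall 14–19 of 30, or 47–63%.
- Wave 3: 31 − 29 = 2 at most, then 0.
- Wave 4: 0.

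| Recall days | Wave 2 | Wave 3 | Wave 4 |
|---|---|---|---|
| Before day 1 | 14–19 | 0–2 | 0 |
| Days 1–28 | 11–16 | 22–28 | 0–2 |
| After day 28 | 0 | 0–8 | 28–30 |

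Counted from the first topic message on day 2, the pre-message days are 15–20, 0–3 and 0.

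**Step 2: is the wave 2 comparison biased?** Write the count as pre-message days of use plus post-message days of use. The expected difference between arms is then the sum of the two differences. Assignment took place at the start of the trial, so the first difference is zero in expectation and the second is the program's effect on the days it could reach. If the program does nothing, both are zero. The estimate is valid for reported 30-day use, and the type I error rate does not change.

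**Step 3: how much smaller is it?** This needs an assumed profile for the daily effect.

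- *Constant from day 1.* Wave 2 shows 11/30 to 16/30 = 37–53% of the full-window effect and wave 3 shows 28/30 to 30/30 = 93–100%. With the same counting rule at both waves and no true growth, the wave 3 to wave 2 ratio runs from 29/16 = 1.8 to 30/11 = 2.7.
- *Constant from day 2.* Wave 2 shows 10/30 to 15/30 = 33–50%. The ratio runs from 28/15 = 1.9 to 30/10 = 3.0.
- *Linear build from day 2 to full strength on day 27*, with daily effect (*d* − 1)/26. The lowest wave 2 value is (1 + … + 10)/26/30 = 0.071 and the highest is (1 + … + 15)/26/30 = 0.154. Wave 3 gives 0.483–0.731 and wave 4 gives 1.00.

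The last case matters for the choice of remedy. Wave 4 would exceed wave 3 by a factor of 1/0.731 = 1.4 to 1/0.483 = 2.1, so waves 3 and 4 are not on one footing either.

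**Step 4: power, as illustration only.** The plan's own figure reproduces: a two-sample t-test at d = .28 with 80% power needs 202 per arm; 202/0.8 = 252.5, rounded up to 253; 2 × 253 = 506. The documents give no effect size or standard deviation for the counts. If a full-window effect on them had 80% power (noncentrality 2.80) and the standard error were unchanged, power at share *s* is Φ(2.80*s* − 1.96) + Φ(−2.80*s* − 1.96). This gives 15.4% at 10/30, 17.7% at 11/30, 28.8% at 15/30 and 32.1% at 16/30.

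**Step 5: does it spread?** The model has a separate condition effect for each later wave, so a small wave 2 effect does not by itself distort waves 3 and 4. The primary outcome is susceptibility at wave 3, a score of openness to vaping with no recall window.

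**The case for a change.** The best case for acting is that the SAP sets out to model change and gives one effect per wave, so readers will compare the waves. To see the problem they would have to combine the survey days, the message days, the recall period and the scope of the SAP, whereas one sentence in the plan would spare them that. It would cost nothing: the data, the model and the estimate all stay.

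The day counts stand, and so does the caution about reading timing from these outcomes. The need to amend the plan does not. The SAP specifies no comparison of the wave 2 effect with a later one and makes no claim about when an effect appears. The Protocol already calls wave 2 mid-intervention and says that three topics were still to come. Partial exposure at that wave is therefore disclosed for every outcome, and only the consequence of the recall window is left unsaid. The 30-day look-back is part of the outcome's definition, and an analyst writing up the results can state what it covers.

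A stronger remedy, resting conclusions about behavior on waves 3 and 4, would do harm. Recruitment closed in June 2024, and delivery and engagement figures are already reported, so such a rule would demote a specified wave after the event. It would also suggest that waves 3 and 4 are comparable with each other, although wave 3 recall falls mainly within messaging and wave 4 recall almost wholly after it.

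Whether the counts are analyzed as days or on the five-point scale that the Protocol ascribes to secondary outcomes is a separate question.

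**Conclusion.** No change to the plan. At wave 2, 14–19 of the 30 recall days precede the first message, so the effect on these counts is probably smaller than a full-window effect: 33–53% of it under a constant daily effect from day 1 or day 2. That is a matter of interpretation for one early time point on secondary outcomes. The estimate is valid, creates no false positive, and leaves waves 3 and 4 and the primary outcome untouched. A label would alter no result.

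If the authors wish, the report can carry a neutral footnote giving the share of each wave's window before, during and after messaging, with a caution that effect sizes on these counts are not directly comparable across the three waves.

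This rests on an inference that the 30-day item was asked at wave 2, since the questionnaire is not in the documents. The day counts need no more than that and a counting rule, and both rules are covered. The effect shares also assume that respondents count days literally and that the daily effect keeps one direction; the power figures assume an equal standard error.

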**Impact of E-Cigarette Prevention Messages on Adolescents**

**Statistical Design and Analytic Plan**

**NCT#05985538**

**Version Date: 6/25/2020**

## Statistical Analysis

For all analyses,  $p$ -values will be 2-sided, and statistical significance will be set at  $p < .05$ . Analyses will be conducted using *R* Studio version 2024.12.0+467 with *R* version 4.4.3 (R Project for Statistical Computing).

### *Missing data.*

Analyses will use an intent-to-treat approach that includes all data collected from enrolled participants regardless of trial attrition, with multilevel multiple imputation to handle missingness on covariates and outcomes. We will use the Markov chain Monte Carlo-based joint multilevel imputation package in *R*, *jomo*, to impute 5 multilevel datasets. We will allow 1000 burn-in iterations and will be thinned by selecting every 1000th draw.

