### *Outcome models.*

We will report covariate-adjusted, unstandardized parameter estimates with 95% confidence intervals. All parameter estimates and standard errors will be computed using Rubin's formulae for aggregating multiply imputed results.

We will use a latent curve modeling (LCM) approach to model change in susceptibility and secondary outcomes. We will use a structural equation modeling (SEM) framework due to its increased modeling flexibility relative to generalized linear mixed models (GLMM); GLMMs are nested within SEM such that any GLMM can be estimated as an SEM. In the LCM shown in Equation 1, the random intercept ( $b_{0i}$ ) and slopes ( $b_{1i} - b_{3i}$ ) are latent variables that affect repeated measures ( $\gamma_{li}$ ) through a factor loading design matrix. Study condition ( $Tx_i$ ) and covariates affect the random intercept; study condition also affects the random slopes. Point estimates and standard errors for the ITT effects of study condition for waves  $t = 2, 3$ , and 4 will be calculated using Model Constraints in *Mplus* by summing  $\gamma_{01} + \gamma_{t1}$ . If random slope variances

are not significantly different from zero, we will fix the variance of the random slopes to zero for model parsimony and computation efficiency. Likewise, we will constrain the variances of the time-varying residuals to equality:  $\sigma_t^2 = \sigma^2$ . See Supplementary Figure A1 for the corresponding path diagram.

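### Five imputations leave avoidable Monte Carlo noise in the week-4 primary verdict; 100 would remove most of it for computing time alone

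*SAP*

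**What the plan says.** The SAP (Missing data) plans joint multilevel imputation of covariates and outcomes and intends "to impute 5 multilevel datasets", with 1000 burn-in iterations and every 1000th draw kept. Under Outcome models it adds: "All parameter estimates and standard errors will be computed using Rubin's formulae for aggregating multiply imputed results". It does not say whether tests then use a t or a normal reference. Under Statistical Analysis, p-values are two-sided "and statistical significance will be set at" p < .05. No reason for five, no seed and no Monte Carlo error criterion is given.

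The protocol (Primary outcome) states: "Susceptibility to vaping at the end of text messaging (wave 3 survey, at 4 weeks) was the primary trial outcome". Outcomes are imputed, so this result depends on the imputation draw. On size, the protocol (Participants) states: "Our target sample size was 506, accounting for up to 20% loss to follow-up". It continues: "The trial had 80% power to detect an effect size of" d = .28. It then reports 480 "adolescents and young adults enrolled in the trial".

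**The concern.** Multiple imputation adds random noise to the pooled estimate and its standard error, and the noise shrinks as the number of imputations m grows. With m = 5 the between-imputation variance is estimated on 4 degrees of freedom, so its coefficient of variation is sqrt(2/4) = 71%; with m = 50 it is sqrt(2/49) = 20%. The single primary verdict at p < .05 could therefore turn on the seed rather than on the data. The plan does not say which of several equally legitimate runs counts. A little power is also given away.

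**Working it through.** **The plan's own figure.** Per arm, n = 2(1.960 + 0.842)²/0.28² = 200.2, so 201; in total 402; allowing for 20% loss, 402/0.8 = 502.5, so 503. The t-based version gives 202 per arm and 404/0.8 = 505. Both are close to 506. With 506 × 0.8 = 404.8 completers, power is 80.4%. The planning figures hold together.

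**Assumed missing information.** The documents give only a planning maximum for loss. For loss d at wave 3 and correlation r between the missing value and the rest of a participant's data, the variance relative to complete data is V = r² + (1 − r²)/(1 − d), and FMI = 1 − 1/V.

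- A: d = .10, r = .7. V = .49 + .51/.9 = 1.057; FMI = .05.
- B: d = .20, r = .6. V = .36 + .64/.8 = 1.160; FMI = .14.
- C: d = .20, r = 0. V = 1/.8 = 1.250; FMI = .20. This is a ceiling for 20% loss, because it treats the other waves as useless.

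**Model.** Set the many-imputation variance to 1, with between part B = FMI and within part U = 1 − FMI. Around the many-imputation z, the pooled estimate is N(z, B/m), and the estimated between variance is b = B·χ²(m−1)/(m−1). Then T = U + (1 + 1/m)b, df = (m−1)[1 + U/((1 + 1/m)b)]², and the test is a two-sided t test. For power, z is centred at 0.28·sqrt(N/V)/2, with equal arms assumed: 3.064, 2.924 and 2.817 at N = 506.

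**A case by hand.** Take C with a many-imputation p of .04, so z = 2.054. With m = 5 the estimate's Monte Carlo SD is sqrt(.20/5) = .20. At the expected b, T = .80 + 1.2 × .20 = 1.04 and df = 4(1 + .80/.24)² = 75, so the critical value is 1.992 and the estimate must exceed 1.992 × sqrt(1.04) = 2.03. The chance of falling short is Φ((2.03 − 2.054)/.20), about 45%. Letting b vary, simulation gives 44%.

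**Results** (simulation, t reference; repeat runs differ by about 0.1 point on the disagreement rates):

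| | A | B | C |
|---|---|---|---|
| Two seeds disagree, N = 506, m = 5 | 2.9% | 6.2% | 9.3% |
| same, m = 50 | 0.9% | 1.7% | 2.4% |
| same, m = 100 | 0.6% | 1.2% | 1.6% |
| p = .04 crosses .05, m = 5 | 22–24% | 39% | 44% |
| same, m = 100 | 0% | 1.6% | 4.4% |
| p = .02 crosses .05, m = 5 | about 0% | 7% | 14% |
| p = .01 crosses .05, m = 5 | 0% | 1% | 4% |
| Power, N = 506: many imputations | 86.5% | 83.2% | 80.4% |
| Power, N = 506: m = 5 | 86.1% | 81.6% | 77.5% |

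At the enrolled N = 480, two m = 5 runs disagree in 3.1%, 6.7% and 9.7% of trials, and power goes from 84.7%, 81.3% and 78.3% to 84.2%, 79.6% and 75.4%. With m = 50 or more, the power loss is at most 0.3 points. Type I error with m = 5 is .050 with t, and .050, .052 and .053 with a normal reference.

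**How far from .05 the noise reaches.** At 80% power, p lies between .03 and .06 in 8.5% of trials. Two independent runs can disagree at most half the time, so that window can supply at most about 4.3 points. At the same 80% power, total disagreement is 3.5%, 7.0% and 9.4%, so in B and C much of it must arise elsewhere. At N = 506, about 45% of disagreements in B and 58% in C come from outside the window.

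**The case against.** The case for leaving five alone is fair. Rubin's rules allow for a finite m, so the test keeps its level, and two runs agree in about 91% to 97% of trials. The FMI is unknown and may be lower than assumed: the same three-item scale is measured four times in about ten weeks, and with r = .8 the formula gives FMI .04 at 10% loss and .08 at 20%. No Monte Carlo error target singles out 100; m = 20 already gives 1.4%, 2.8% and 3.9% disagreement, and m = 50 recovers nearly all the power. All of this stands. It limits the size of the point and leaves the exact number a matter of judgement. It does not show that five is as good as 100.

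Two further objections also stand. Many more fits mean more chances of non-convergence and more dataset-specific decisions, since the SAP says of non-significant slope variances: "we will fix the variance of the random slopes to zero for model parsimony and computation efficiency". And the number can no longer simply be called fixed in advance. The protocol reports recruitment closed in June 2024 and gives week-2 and week-4 engagement answers by arm, and the SAP cites sources accessed in April 2025.

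A reader might infer that five imputations make the primary test invalid or inflate type I error. The calculation does not support this, and nothing in the documents points to it. A reader might also infer from the timing that the primary result was known when five was chosen. The documents show engagement by arm, not susceptibility by arm, so that does not follow.

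**Conclusion.** The point holds as a cheap improvement of minor to moderate weight, not as the correction of an error. With m = 5 the seed decides the primary verdict in roughly 3% to 9% of trials over the assumed FMI range, against 0.6% to 1.6% with m = 100. Results with p of .01 or less are nearly safe; those at .02 are not always. The power loss of about 0.5, 1.6 and 2.9 points is secondary, and it would be too strong to say that it defeats the design: at N = 506, A and B stay above 80%, and only the ceiling scenario drops below.

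The statement that type I error stays at .050 assumes a correct imputation model, data missing at random and Rubin's t reference. The SAP does not list the terms of the imputation model, and the calculation does not test it. The sizes rest on assumed loss and correlation and on a large-sample normal model. Even m = 100 cannot settle a p-value lying exactly on .05.

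**What to change.** In the SAP's missing-data section, replace 5 by 100 imputed datasets and keep the stated burn-in and thinning. Under Outcome models, state that tests and 95% confidence intervals use Rubin's t reference. Set the number and the seed without reference to the p-value; a seed makes the run repeatable but does not reduce Monte Carlo error. If the five-imputation result has already been seen, disclose the change and report both the m = 5 and the m = 100 results. Reporting the FMI and Monte Carlo error of the week-4 contrast would be useful, but the point does not depend on it.

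The cost is computing time. One imputation run grows from about 5,000 to about 100,000 sampler iterations. The documents imply about 29 models (1 primary outcome, 19 secondary outcomes, 8 moderators, 1 baseline-susceptibility model). If all use the same imputations, that is at least 29 × 100 = 2,900 fits instead of 29 × 5 = 145, and more where slope variances are fixed and models refitted. A rule for non-converged fits should be written down. No data, participants or model terms change.
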